Because of our promising pilot work,¹ we believe it is appropriate to choose suicidal ideation as our primary outcome. In our pilot study, which included nine Veterans undergoing the VA BIC intervention, we found a greater than five-point improvement in the Beck Scale for Suicidal Ideation (BSS) over the three months following inpatient mental health discharge. Five points is a clinically meaningful improvement on the BSS as it represents the mean difference in suicidal ideation between ambulatory and hospitalized psychiatric patients.² Furthermore, with this sample size and level of improvement, we were able to demonstrate a significant difference in improvement in suicidal ideation compared to a matched group of historical controls participating in a post-mental health discharge qualitative study.³ Therefore, we believe that we will have sufficient power to show a clinically meaningful improvement in suicidal ideation overall and for each of the four high-risk care transition scenarios at one and three months after discharge if we enroll a total of 100 veterans (25 per transition scenario) over 3 years. We will also assess other important measures of suicide risk including hopelessness, connectedness, fatal/non-fatal suicide attempts and treatment engagement.⁴⁻⁷ Please see the Assessment Manual for all assessment templates (see **Appendix 2**). We will assess post-discharge treatment engagement by evaluating continuity of care and disruptions of care (including missed appointments). We will abstract these data from the electronic medical record. In addition, we will ask veterans to report on any treatment they may have received outside of the VA healthcare system. We will use a standardized data

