We will perform a more complex analysis for the entire study sample at the end of the four years because we will have adequate power to do so. The following outlines are specific approach: Based on available evidence, we hypothesize that the VA BIC program plus standard hospital discharge care will lead to a significant reduction in suicidal ideation after discharge from an acute care setting. We believe that the effect of VA BIC on suicidal ideation will be the greatest at the three-month follow-up because the greatest intensity of follow-up care provided through VA BIC occurs within the first three months after discharge. We will generate descriptive summary statistics (e.g., means and standard errors, medians) and graphical displays for the BSS total scores at baseline and at each of the follow-up assessments. Because BSS scores are typically over dispersed, it is not appropriate to use standard parametric statistics. Therefore, we will treat the BSS scores as count data and use negative binomial regression. Specifically, we will use a generalized linear mixed model. We will consider allocation of study arm (categorical measure) and time (continuous measure) as fixed effects. Random effect will be used to account for correlation that arises from repeated measures of the same individual. We will assume a linear effect and model changes in suicidal ideation over time. We will calculate 95% CI and P-values and will define a *P*-value of < 0.05 to be statistically significant. We will use the maximum likelihood ratio to account for any missing data.

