Sample Size: Because of our promising pilot work,¹ we believe it is appropriate to choose suicidal ideation as our primary outcome. In our pilot study, which included nine Veterans undergoing the VA BIC intervention, we found a greater than five-point improvement in the Beck Scale for Suicidal Ideation (BSS) over the three months following inpatient mental health discharge. Five points is a clinically meaningful improvement on the BSS as it represents the mean difference in suicidal ideation between ambulatory and hospitalized psychiatric patients.² Furthermore, with this sample size and level of improvement, we were able to demonstrate a significant difference in improvement in suicidal ideation compared to a matched group of historical controls participating in a post-mental health discharge qualitative study.^{1,3} Therefore, we will have sufficient power to show a clinically meaningful improvement in suicidal ideation overall and for each of the four high-risk care transition scenarios at one and three months after discharge if we enroll a total of 100 veterans (25 per transition scenario) over 3 years.

Study Population and Recruitment

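### The claim of sufficient power within each 25-patient scenario has no stated basis, and no planned analysis compares the effect of VA BIC between scenarios

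*Combined protocol and SAP*

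**What the plan says.** Statistical Considerations, Sample Size, says of the four scenarios, with 25 veterans in each and 100 in total: "we will have sufficient power to show a clinically meaningful improvement in suicidal ideation overall and for each of the four high-risk care transition". The claim covers both the one-month and the three-month visit. Specific Aims/Purpose and Preliminary Studies say the same as a belief: "Therefore, we believe that we will have sufficient power to show a clinically meaningful improvement in suicidal ideation overall", and likewise for each scenario.

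Two facts are offered in support. The first is the pilot, "which included nine Veterans undergoing the VA BIC intervention, we found a greater than five-point improvement" on the BSS over three months. The second is that "we were able to demonstrate a significant difference in improvement in suicidal ideation compared to a matched group of historical controls". Five points is called clinically meaningful because it is the mean difference between ambulatory and hospitalized psychiatric patients.

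On analysis, Specific Aim 1 under Statistical Considerations plans a repeated measures ANOVA in each setting, followed by two-sample t-tests if the ANOVA is significant. A more complex analysis is planned "for the entire study sample at the end of the four years because we will have adequate power to do so". That analysis is a negative binomial mixed model, chosen as follows: "Because BSS scores are typically over dispersed, it is not appropriate to use standard parametric statistics". Its terms are described thus: "We will consider allocation of study arm (categorical measure) and time (continuous measure) as fixed effects". The plan adds: "We will assume a linear effect and model changes in suicidal ideation over time".

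Specific Aims/Purpose says that evaluating the four scenarios will point rural facilities to the populations with most to gain. The Year 4 deliverables integrate and analyse the data across scenarios but name no comparison between them.

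**The concern.** Power for a randomized comparison needs a between-arm difference and a measure of spread. The pilot improvement is a change within treated patients, and controls may also improve after discharge. The historical-control result is reported only as significant. The five-point benchmark is a difference between two patient populations, not a treatment effect. A reader therefore cannot tell whether 25 per scenario is enough.

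The second difficulty is the question the scenarios are meant to answer. Four separate tests show which scenarios reach P < 0.05. They do not show that the effect differs between scenarios. The pooled model as listed has no setting term, so it cannot show this either.

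Specific Aims/Purpose makes later dissemination depend on VA BIC being effective in at least one scenario. With about 12 v 13 patients, a non-significant scenario could be read as a setting where VA BIC does not work. A mix of significant and non-significant scenarios could be read as a real ranking.

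**Working it through.** **Reproducing the plan's figure.** This is not possible. The documents give the sample size, equal allocation, the 0.05 level and the 0 to 38 scale range. They give no SD, between-arm difference, power level, sidedness or dropout rate.

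**Conditional check.** Assumptions that are not in the documents: between-arm t-test at one visit, two-sided 0.05, common SD, no dropout, SD between 4 and 10 points. The Specific Aim 1 t-tests can also be read as comparing visits, so this is a generous reading.

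For 12 v 13, SE = SD × √(1/12 + 1/13) = 0.400 SD, with 23 degrees of freedom. Power comes from the noncentral t distribution with noncentrality = difference/SE.

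| Comparison | Detectable at 80% power |
|---|---|
| 12 v 13, unadjusted | 1.17 SD |
| 12 v 13, baseline-adjusted, assumed correlation 0.5 | about 1.04 SD |
| 10 v 10, unadjusted (20% lost) | 1.33 SD |
| 50 v 50, pooled | 0.57 SD |
| 40 v 40, pooled (20% lost) | 0.63 SD |

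The adjusted row multiplies the SD by √(1 − 0.5²) = 0.866, uses 22 degrees of freedom, and inflates the variance by 1 + 1/(25 − 4) for chance baseline imbalance.

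Power in one scenario, if the true between-arm difference were 5 points:

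| Assumed SD | Unadjusted | Adjusted |
|---|---|---|
| 4 | 85% | 92% |
| 5 | 67% | 77% |
| 7 | 40% | 49% |
| 10 | 22% | 27% |

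Unadjusted power reaches 80% only if the SD is at most 5/1.171 = 4.3. If controls also improved and the difference were 3 points, unadjusted power at the same SDs would be 43%, 30%, 18% and 11%. The unadjusted 95% CI half-width for one scenario is 2.069 × 0.400 = 0.83 SD.

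**Dependence on the model.** These t-test figures only approximate the planned count model. A rough single-visit negative binomial check assumed a control mean of 7 to 12, a treated mean 5 lower, and variance = mean + mean²/k with k from 0.5 to 2. Power ranged from 15% to 93% for 12 v 13, and from 46% to over 99% for 50 v 50. The answer rests on inputs that the plan does not state.

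**Reading four tests side by side.** For illustration only, take one between-arm t-test per scenario with no preceding ANOVA, and an identical 5-point effect in all four. With per-scenario power p, the chance of some but not all being significant is 1 − p⁴ − (1 − p)⁴. At SD 5, p = 0.667 and the result is 79%. All four are significant 0.667⁴ = 20% of the time. With no effect anywhere, the chance that at least one scenario is significant in favour of VA BIC is 1 − 0.975⁴ = 9.6%.

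**Comparing two scenarios directly.** The SE is √2 times larger: SD × √(2 × (1/12 + 1/13)) = 0.566 SD. On this linear scale, power for a 5-point difference between two scenario effects is 59% at SD 4 and 42% at SD 5. A direct comparison is the right one, but it will be imprecise.

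**The case against.** The strongest reply is that the trial may be adequately powered. At an SD of about 4.3 or less, 25 patients give 80% power for 5 points, and baseline adjustment helps further. That stands. A reader might infer that the scenarios are underpowered, but the documents do not show this, because they give no SD.

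A reader might also infer that the plan contradicts itself, since it holds the complex model back until the whole sample is available on grounds of power. That wording may mean only that a mixed count model needs more data than a simple test, so it does not prove a contradiction. Using ANOVA and t-tests within settings for a score that the plan considers unsuited to parametric methods is a real tension. It is a separate matter, but it bears on which method should produce the scenario estimates.

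The promise in Specific Aims/Purpose can be read loosely, as naming the settings where VA BIC is shown to work. That is a fair reading, and softening the sentence is a legitimate remedy. It still does not allow a significant setting to be ranked above a non-significant one.

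The consequences can be overstated. The deliverables contain no go/no-go rule, the later trials follow regardless, and the integrated manual covers all four scenarios. Finalising the inpatient manual in Year 2 on the basis of results may concern only its content. The main route to harm is the condition that VA BIC be effective in at least one scenario.

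Finally, the mixed-picture figure is not a property of the written plan, which puts an ANOVA before the t-tests and leaves open what they compare. It illustrates a risk.

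**Conclusion.** The concern holds in two parts. First, sufficient power in each scenario is asserted without the inputs that would support it. The claim is unsupported rather than false. Under the stated t-test assumptions a scenario of 25 detects about 1.17 SD (1.04 SD with baseline adjustment at correlation 0.5), against 0.57 SD for the pooled sample. For 5 points, per-scenario power runs from 85% to 22% unadjusted as the assumed SD goes from 4 to 10.

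Second, no analysis is specified that could show whether the effect differs between scenarios, although the plan promises guidance on who gains most. Differences in significance cannot fill that gap.

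Both parts rest on what the documents state and omit. The numbers rest on assumed SDs, an assumed correlation and a t-test approximation.

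**What to change.** 1. **Power statement, now.** In Specific Aims/Purpose, Preliminary Studies and Sample Size, delete the claim of sufficient power for each scenario. In Sample Size, state the detectable pooled and per-scenario differences with their assumptions: a BSS SD or range with its source, the sponsor's expected dropout, power level and sidedness. Say that t-test figures approximate the count model, whose power depends on further inputs.
2. **Conclusions.** Base the effectiveness conclusion on the pooled comparison. Report each scenario, including in the yearly analyses, as a between-arm estimate with a 95% CI and not as a pass/fail test. Name a method consistent with the plan's own view of BSS, such as the same count model or a baseline-adjusted difference with a bootstrap CI.
3. **Pooled model.** Add setting, and make the between-arm effect at follow-up estimable. One form uses baseline BSS as a covariate with arm, visit, arm-by-visit, setting and arm-by-setting terms on the follow-up scores. The other keeps baseline as an outcome and adds arm-by-time and arm-by-time-by-setting terms with their lower-order terms. In the second form, arm-by-setting alone is not enough. On a linear scale with balanced visits, between-arm differences of 0, 5 and 5 points at 0, 1 and 3 months would average to 10/3 = 3.3.
4. **Scale and status.** A log-link model compares ratios, while the benchmark is in points. Prespecify setting-specific effects as model-based mean BSS point differences as well as ratios, with CIs. Label the between-setting comparison exploratory and imprecise, and rest any statement about who gains most on it. Otherwise, soften the promise in Specific Aims/Purpose.

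**Cost.** The power statement becomes less favourable. The model gains 8 parameters in the covariate form (baseline 1, arm-by-visit 1, setting 3, arm-by-setting 3), 14 if setting effects are visit-specific, or 13 in the baseline-as-outcome form with linear time. With 100 patients the smaller form is easier to fit. No patients or visits are added. Only Ground East is opening now, so items 3 and 4 can be settled by amendment before the later scenarios open.
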